9.2 Supportive Care

The following are the supportive care guidelines for the study:

9.2.1 Hyperphosphataemia prevention

- All treated patients should receive adequate instructions concerning dietary phosphate restriction. The main natural sources of phosphate are:
 - Dairy products (milk, cheese, ice-cream, yogurt)
 - Meat
 - Dried beans
 - Peas
 - Nuts and peanut butter
 - Wholegrains
 - Cola
- During the dose-escalation phase of the debio 1347 trial, only 50% of patients needed to be treated with phosphate chelators. In the expansion phase, three patients did receive prophylactic sevelamer, and there was no clear difference with regard phosphate levels in these patients. In view of the side-effects associated with use of phosphate chelators, prophylaxis *will not be required* in phase 2 portion of the study. Phosphate levels will be measured on cycle 1 D4 (+/-1 day), and treated according to the guidelines provided in section 9.4.2. At the time of this amendment, all patients on the phase 1 cohort were off study.

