Febrile neutropenia, Neutropenia with infection	4	Permanent discontinuation	Permanent discontinuation
	3	Permanent discontinuation	Temporary discontinuation until recovery to Grade 0
Neutropenia	3, 4	Temporary discontinuation until recovery to Grade 2	Temporary discontinuation until recovery to Grade 2
Thrombocytopenia	4	Permanent discontinuation	Temporary discontinuation until recovery to Grade 1
	3	Temporary discontinuation until recovery to Grade 1 Permanent discontinuation if a platelet	If a platelet transfusion is required, temporary

Adverse Event	Grade	Action	
		transfusion is required	discontinuation until recovery to Grade 1
Diarrhea, constipation, nausea, vomiting	3,4	Permanent discontinuation, if not manageable by optimal symptomatic therapy	Temporary discontinuation until recovery to Grade 2, or baseline
Skin toxicity (See additional guidelines in 9.4.1)	3,4	Permanent discontinuation, if not manageable despite prophylaxis and optimal symptomatic therapy	Temporary discontinuation until recovery to Grade 2, or baseline
Hyperphosphataemia		Please use the treatment guidelines per 9.4.2	Please use the treatment guidelines per 9.4.3
Hypertension	4	Permanent discontinuation	Permanent discontinuation
	3	Permanent discontinuation	If uncontrolled, temporary discontinuation until control is achieved
Hepatotoxicity (AST, ALT, ALP, γ GTP increased)	4	Permanent discontinuation	Permanent discontinuation
	3	Temporary discontinuation, until recovery to Grade 2	Temporary discontinuation, until recovery to Grade 2
Other non-haemotoxicity (except for transient electrolyte abnormalities)	4	Permanent discontinuation	Permanent discontinuation
	3	Permanent discontinuation	Temporary discontinuation until recovery to Grade 1 or baseline
Recovery from above AEs		Permanent discontinuation, if failure to recover within 7 days, otherwise treatment at same dose level. Dose reduction during the DLT has to be discussed with the PI	Permanent discontinuation, if failure to recover within 14 days, otherwise retreatment at next lowest dose level

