9.4.2 Hyperphosphatemia (Phase I)

1. Initial Modifications on Treatment:

Serum phosphorus level	
5.5 – 6.9 mg/dL	
 1. Continue Debio 1347 2. Continue (or increase) sevelamer powder 2400mg TID 3. Add Fosrenol 1g TID 4. Recheck within 7 days

≥ 7 mg/dL	
 1. Hold Debio 1347 2. Continue (or increase) sevelamer powder 2400mg TID 3. Add Fosrenol 1g TID 4. check within 7 days -> resume if Ph < 5.5 and recheck within 7 days of resumption
----------------	---

*If sevelamer is not available or tolerable, alternate phosphate reducing agents or preparations can be utilized.

2. Second Modification on Treatment

Serum phosphorus level	
5.5 – 6.5 mg/dL	
 1. Cont Debio 1347 2. Cont sevelamer powder to 2400mg TID increase Fosrenol to 1.5mg TID 3. recheck within 7 days
6.6-6.9mg/dL	
 1. Cont Debio 1347 2. Cont sevelamer powder to 2400mg TID 3. Cont Fosrenol 1g TID 4. add acetazolamide 250mg BID 5. recheck within 7 days
≥ 7 mg/dL	
 1. Hold Debio 1347 – consider dose reduction 2. Cont sevelamer powder to 2400mg TID 3. increase Fosrenol to 1.5g TID 4. add acetazolamide 250mg BID 5. check within 7 days -> resume if Ph < 5.5

*If sevelamer is not available or tolerable, alternate phosphate reducing agents or preparations can be utilized.

3. Subsequent Modifications:

Serum phosphorus level	
> 5.5 mg/dL-6.9mg/dL	
 1. If not already, maximize regimen to include: sevelamer powder to 2400mg TID fosrenol to 1.5g TID acetazolamide 250mg BID 2. If already maximized, consider dose reduction (without interrupting drug) 3. Recheck within 7 days
≥ 7 mg/dL	
 1. Hold Debio 1347 – dose reduction needed 2. Maximize regimen to include: sevelamer powder to 2400mg TID fosrenol to 1.5g TID acetazolamide 250mg BID

	3. check within 7days -> resume with dose reduction if Ph < 5.5
--	---

*If sevelamer is not available or tolerable, alternate phosphate reducing agents or preparations can be utilized.

- For patients whose phosphorous control improves after Debio 1347 dose reductions, escalation of the phosphorus regimen can be considered at the discretion of the investigator. Subsequent to any such adjustment, phosphorous level should be rechecked within 7 days.

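### Section 9.2.1 sends the Phase II cycle 1 day 4 phosphate result to the Phase I treatment table (9.4.2) instead of the Phase II table (9.4.3), and the two differ at a first level of 5.5-6.9 mg/dL

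*Combined protocol and SAP*

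**What the plan says.** Section 9.2.1 explains why binder prophylaxis is no longer required in the phase 2 portion, giving as one reason: "In view of the side-effects associated with use of phosphate chelators". The day 4 instruction follows at once: "Phosphate levels will be measured on cycle 1 D4 (+/-1 day), and treated according to the guidelines provided in section 9.4.2". The closing sentence of the same bullet reads: "At the time of this amendment, all patients on the phase 1 cohort were off study".

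The protocol has two hyperphosphataemia tables. Section 9.4.2 is headed for Phase I and section 9.4.3 for Phase II. In Table 1 of section 9.4, the column for the Phase I DLT period refers to 9.4.2. The column that covers Phase I outside the DLT period and all of phase 2 says: "Please use the treatment guidelines per 9.4.3".

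At a first level of 5.5-6.9 mg/dL, 9.4.2 orders "Continue (or increase) sevelamer powder 2400mg TID" and then "Add Fosrenol 1g TID" (Fosrenol is lanthanum carbonate). For the same level, 9.4.3 starts sevelamer at 1200 mg three times daily, raises it to 2400 mg three times daily if tolerated, and gives no lanthanum at that step. Its notes require sevelamer and lanthanum to be taken at least 2 hours after or 4 hours before Debio 1347.

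**The concern.** The day 4 test is the first phosphate check after dosing starts, and every Phase II patient is scheduled to have it. The sentence that tells the clinician what to do with the result names the wrong table. This is a live treatment instruction, not background text.

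A clinician who follows the pointer at 5.5-6.9 mg/dL would aim at full-dose sevelamer plus a second binder from the start, where the Phase II table begins with half that sevelamer dose alone. The same clinician would find no instruction to separate the binders from Debio 1347. The general 2-hour rule in sections 9.1.1 and 9.2.2 is written for drugs that alter gastric pH and does not name sevelamer or lanthanum. At stake are avoidable binder exposure, which the protocol was trying to limit, and loss of the spacing rule for an oral study drug.

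**Working it through.** No statistical figure is involved. The check is a comparison of texts plus daily-dose arithmetic.

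**Step 1: whom the sentence reaches.** The sentence before it is about the phase 2 portion, and the sentence after it says the Phase I cohort was off study. Only Phase II patients remain.

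**Step 2: which table governs them.** The 9.4.3 heading and the phase 2 column of Table 1 both give 9.4.3. Day 4 lies within what would be the DLT window, but the Table 1 column that refers to 9.4.2 is confined to the Phase I part, and section 9.3 defines DLTs for Phase 1 only. The calendar day therefore does not bring a Phase II patient under 9.4.2.

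**Step 3: first-step orders side by side.** Daily dose = single dose x 3.

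| First level | 9.4.2 (Phase I) | 9.4.3 (Phase II) |
|---|---|---|
| 5.5-6.9 mg/dL, Debio 1347 | continue | continue |
| 5.5-6.9, sevelamer | 3 x 2.4 g = 7.2 g/day | 3 x 1.2 g = 3.6 g/day, to 3 x 2.4 g = 7.2 g/day if tolerated |
| 5.5-6.9, lanthanum | 3 x 1 g = 3 g/day | none at this step |
| 7 mg/dL or more | hold; sevelamer 7.2 g/day; lanthanum 3 g/day; resume below 5.5 | the same in substance |
| Spacing from Debio 1347 | none stated | 4 h before + 2 h after = 6 h without binder around each daily dose |

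**Step 4: size of the difference at 5.5-6.9 mg/dL.** At the start, sevelamer is 7.2 / 3.6 = 2 times as high under 9.4.2, and lanthanum differs by 3 - 0 = 3 g/day. Once sevelamer is fully titrated under 9.4.3, the sevelamer difference is 7.2 - 7.2 = 0 and the 3 g/day of lanthanum remains.

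**Step 5: how long it lasts.** Section 9.4.3 rechecks phosphate within 7 days, by about day 4 + 7 = day 11. If the level is still 5.5-6.9 mg/dL, its second step brings in lanthanum 1 g three times daily alongside sevelamer 2400 mg three times daily. For those patients the lanthanum gap is about a week. For patients who fall below 5.5 mg/dL on sevelamer alone, 9.4.3 does not call for lanthanum at that recheck.

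**Step 6: how many patients.** The planned 18 to 43 Phase II patients have the test. The documents do not give the share at 5.5-6.9 mg/dL on day 4, so the affected number cannot be estimated.

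**The case against.** The strongest reply is that this is a slip in one digit which the protocol already resolves. Both headings name their phase, Table 1 gives the right section, and 9.4.3 begins directly after 9.4.2. That stands: 9.4.3 is plainly intended, and a careful reader will find it. It limits the harm to readers who follow the pointer, but 9.2.1 is where the day 4 test is described, so that is the pointer they will meet.

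A second reply is that 9.4.2 is not a clean order for a Phase II patient. Its sevelamer line speaks of continuing or increasing, which presupposes the dropped prophylaxis. This also stands, and the mismatch may alert the reader. It does not apply to the lanthanum line, which simply adds the drug, or to the missing spacing rule.

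A third reply is that prophylaxis and treatment are different things: dropping binders for patients with normal phosphate does not make fuller treatment of raised phosphate contrary to the plan. That is fair. The point rests on the conflict between the two tables, not on the reason for dropping prophylaxis.

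A reader might infer that the error changes Debio 1347 dosing. It does not: at 5.5-6.9 mg/dL both tables continue the drug, and at 7 mg/dL or more both hold it and resume below 5.5 mg/dL. Nor is day 4 the first phosphate measurement of any kind, because phosphate is also measured at screening and in the cycle 1 day 1 chemistry panel.

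**Conclusion.** The cross-reference in 9.2.1 is wrong as written and should be corrected. Its consequence is confined to Phase II patients whose first level is 5.5-6.9 mg/dL and whose clinician follows the pointer. For them, 9.4.2 calls for twice the starting sevelamer dose (7.2 against 3.6 g/day), adds lanthanum 3 g/day one step early, and omits the binder spacing. The dose difference narrows as sevelamer is titrated, and the lanthanum difference can close at the recheck within 7 days if phosphate is still 5.5 mg/dL or above.

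The documents do not support reading this as a threat to the efficacy result. Nothing in it alters the clinical benefit endpoint, the stage sizes of 18 and 43 or the decision limits, and no effect on the Simon decision follows. The conclusion assumes only that the day 4 sentence applies to Phase II patients, which its neighbouring sentences establish.

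**What to change.** In section 9.2.1, replace the reference to section 9.4.2 with section 9.4.3 in the sentence on the cycle 1 day 4 phosphate measurement. Nothing else is needed for this point: 9.4.3 already contains the starting dose, the titration, the recheck and the spacing rule. The cost is one changed section number in the next amendment, with no added visits, tests or patients.

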9.4.3 Hyperphosphatemia (Phase II)

INITIAL TREATMENT MODIFICATION	
Serum Phosphorous Level	Intervention/Modification
5.5 – 6.9 mg/dL	
 Continue treatment with Debio 1347 at current dose AND Start on sevelamer oral POWDER 1200mg three times a day (subjects may use tablets if preferred, but tends to have more gastrointestinal toxicity) Escalate to sevelamer oral POWDER or tablets 2400mg three times a day if tolerated. Reassess serum phosphorus within 7 days
≥ 7 mg/dL	
 Hold treatment with Debio1347 Start sevelamer oral POWDER or tablets 2400mg three times a day Add treatment with lanthanum carbonate (Fosrenol®) 1g three times a day Reassess serum phosphorus level within 7 days: 
 If serum phosphorus level < 5.5 mg/dL, resume Debio 1347 at same dose and recheck within 7 days of resumption
Note:	
 Sevelamer should be preferably taken in the middle of meals Lanthanum carbonate should be taken just after meals Sevelamer and lanthanum must be administered at least 2 hours after or 4 hours before Debio 1347

SECOND TREATMENT MODIFICATION	
Serum Phosphorous Level	Intervention/Modification
5.5 – 6.5 mg/dL	
 Continue treatment with Debio 1347 at a current dose AND Continue sevelamer oral POWDER or tablets 2400mg three times a day Introduce treatment with lanthanum carbonate (Fosrenol®) to 1.0g three times a day or increase to 1.5g three times a day Reassess serum phosphorus level within 7 days
6.6-6.9 mg/dL	
 Continue treatment with Debio 1347 at current dose AND Continue sevelamer oral POWDER or tablets 2400mg three times a day Introduce treatment with lanthanum carbonate (Fosrenol®) to 1.0g three times a day or increase the dose to 1.5g three times a day Add treatment with oral acetazolamide 250mg twice a day Reassess serum phosphorus level within 7 days
≥ 7 mg/dL	
 Hold treatment with Debio 1347 – consider dose reduction Continue sevelamer oral POWDER or tablets 2400mg three times a day Increase treatment with lanthanum carbonate (Fosrenol®) to 1.5g three times a day AND

	
 • Add treatment with oral acetazolamide 250mg twice a day • Reassess serum phosphorus level within 7 days: 
 ◦ If serum phosphorus level < 5.5 mg/dL, resume Debio 1347 with dose reduction

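### Section 9.2.1 sends the Phase 2 day 4 phosphate result to the Phase I algorithm, and 9.1.2 bans the phosphate binders that 9.4 orders

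*Combined protocol and SAP*

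**What the plan says.** **Where the day 4 result goes.** Section 9.2.1 states that binder prophylaxis is not needed in Phase 2. It then orders a phosphate measurement on cycle 1 day 4, to be "treated according to the guidelines provided in section 9.4.2", and notes that every Phase 1 patient had already left the study. Section 9.4.2 is titled for Phase I and 9.4.3 for Phase II. In Table 1 of section 9.4, the hyperphosphataemia entry in the column that covers Phase 2 reads "Please use the treatment guidelines per 9.4.3".

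**What the two algorithms order at a first value of 5.5–6.9 mg/dL.**
- 9.4.2: "Continue (or increase) sevelamer powder 2400mg TID" and "Add Fosrenol 1g TID".
- 9.4.3: "Start on sevelamer oral POWDER 1200mg three times a day", then "Escalate to sevelamer oral POWDER or tablets 2400mg three times a day if tolerated". Lanthanum (Fosrenol) is not part of this step.

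Section 9.4.3 also carries a timing rule: "Sevelamer and lanthanum must be administered at least 2 hours after or 4 hours before Debio 1347". Section 9.4.2 has no such rule.

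**Status of binders as concomitant medication.** Section 9.1.2 lists phosphorus absorbers among the drugs excluded during the study. It writes no exception for those ordered in 9.4, and it closes by requiring withdrawal of a patient who needs a prohibited drug. Section 10.1.4 has that decision taken jointly with the Sponsor. Section 12.3.3 leaves out of the efficacy population patients given concomitant treatment that was not permitted, and 9.5 replaces Phase II patients who cannot be evaluated for efficacy.

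**The concern.** The first point is a wrong cross-reference in an operative instruction. Two members of staff holding the same day 4 value could give different binder regimens, depending on whether they followed 9.2.1 or Table 1. The one following 9.2.1 would not see the rule on spacing binders from the study drug. Section 9.2.1 gives the side effects of binders as its reason for dropping prophylaxis, yet its own reference leads to the heavier first-step regimen. This point has no bearing on who is analysed.

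The second point does bear on the analysis, though only under a literal reading. If a binder ordered under 9.4 counted as a prohibited drug, the patient could be withdrawn, dropped from the efficacy population and replaced. That population is presumably the denominator of the clinical benefit rate. Section 14 does not say so: it refers to patients who cannot be evaluated for the efficacy endpoint but does not name 12.3.3. In an open-label single-arm trial, evaluability should not rest on a case-by-case reading of two sections that disagree.

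**Working it through.** The plan gives no figure to reproduce. The check sets the sections side by side and converts the doses to daily totals.

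**1. To whom does the 9.2.1 instruction apply?** The sentence before it concerns Phase 2, and the sentence after it says no Phase 1 patient remained on study. It can therefore only concern Phase 2, for which Table 1 and the section titles give 9.4.3. The two references cannot both be right.

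**2. First-step doses at 5.5–6.9 mg/dL.**
- Sevelamer, 9.4.2: 2400 mg × 3 = 7200 mg/day.
- Sevelamer, 9.4.3 at the start: 1200 mg × 3 = 3600 mg/day. Ratio 7200 / 3600 = 2.0.
- Sevelamer, 9.4.3 after escalation: 2400 mg × 3 = 7200 mg/day. Ratio 1.0.
- Lanthanum, 9.4.2: 1 g × 3 = 3 g/day. Lanthanum, 9.4.3: none.

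**3. Largest cumulative difference before the recheck.** Both algorithms recheck phosphate within 7 days.
- Sevelamer: (7200 − 3600) mg/day × 7 days = 25,200 mg = 25.2 g if the dose is never escalated, and less if it is.
- Lanthanum: 3 g/day × 7 days = 21 g.

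**4. First-step doses at 7 mg/dL or above.** Both algorithms hold Debio 1347 and give sevelamer 2400 mg TID plus lanthanum 1 g TID. The binder doses do not differ.

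**5. Reach of the wrong reference.** It covers the day 4 result only. Phosphate is also in the regular chemistry panel (section 10.1, footnote d), and those later results fall under Table 1 and hence 9.4.3.

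**6. Spacing.** Sections 9.1.1 and 9.2.2 give timing advice for drugs that alter gastric pH but name no phosphate binder. A reader sent to 9.4.2 therefore does not find the rule elsewhere.

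**7. The prohibition.** Section 9.1.1 names no binder, and its general allowance for other medication leaves out whatever is on the excluded list, so it does not supply the missing exception. Section 9.1.2 does write exceptions for other classes, such as bone-directed agents and inhaled corticosteroids. Section 9.4.3, by contrast, opens its first step with "Continue treatment with Debio 1347 at current dose AND" and goes on to start sevelamer. The same patient is thus told to stay on treatment with a binder (9.4.3) and is listed for withdrawal for needing one (9.1.2).

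**8. Number of patients.** Section 9.2.1 reports that 50% of patients in the earlier Debio 1347 dose escalation needed binders, so their use will not be rare. That figure does not give the number who would be in the 5.5–6.9 mg/dL band on day 4, or the number who would be judged to have had a prohibited drug. Neither can be derived.

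**The case against.** On the cross-reference, the best reply is that it corrects itself. A reader who turns to 9.4.2 sees a Phase I title with a Phase II section straight after, and Table 1 is the governing dose-modification table. The 9.4.2 wording also speaks of continuing or increasing sevelamer, which presumes a patient already on it; a Phase 2 patient on day 4 normally is not. This makes the error easier to notice. It does not remove it, because someone who follows 9.2.1 as written still reaches a higher regimen and no spacing rule.

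On the prohibition, the reply is stronger. The protocol orders these drugs by name and dose. The footnotes to 9.4.2 allow other phosphate-lowering agents when sevelamer is unavailable or not tolerated, 9.4.3 offers tablets in place of powder, and the DLT definition in 9.3 presumes phosphorus-lowering treatment. A specific order would normally prevail over an item in a general list. All of this stands as evidence of intent, and it would be too strong to say that the protocol nowhere allows binders. What is missing is narrower: neither 9.1.2 nor 12.3.3 says that binders given under 9.4 are outside the prohibition. The eligibility exclusions in 6.3 name the same drug class, but as an entry criterion, so they do not settle use on study.

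It is also fair that the route from 9.1.2 through 12.3.3 to 9.5 is hypothetical. It should be read as a gap in the wording and not as a forecast of exclusions.

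**Conclusion.** Both inconsistencies hold, and both are minor.

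1. The reference in 9.2.1 is wrong. At a day 4 value of 5.5–6.9 mg/dL it doubles the starting sevelamer dose, a gap that closes if 9.4.3 is escalated. It also adds lanthanum 3 g/day and omits the spacing rule. At 7 mg/dL or above the first-step binder doses agree. The dose comparison assumes that staff would apply 9.4.2 at its stated doses to a patient not yet on sevelamer. The efficacy population is not affected.

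2. Section 9.1.2 conflicts with 9.4 because it has no exception for protocol-ordered binders. An effect on the primary endpoint is unlikely: it requires the general prohibition to be read over the specific orders, and 12.3.3 to be the clinical benefit rate denominator, which Section 14 does not state. Large-scale withdrawal is not expected. How 12.3.3 treats such a patient is nevertheless left to judgement.

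**What to change.** - In 9.2.1, change the reference from 9.4.2 to 9.4.3.
- In 9.1.2, add one sentence: phosphate binders given for hyperphosphatemia under section 9.4 are permitted, and their use is neither a reason for withdrawal nor a ground for exclusion under 12.3.3.

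The cost is amendment wording only. Sample size, procedures and planned analyses stay as they are.

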9.2.2 Gastrointestinal disorders

For nausea, vomiting, diarrhea or constipation, treatment may include anti-emetics, anti-diarrheas or laxative bowel regimen consistent with standard of care. Since drugs that alter gastric pH (e.g., proton pump inhibitors, histamine receptors antagonists, antacids) may

interfere with the absorption of Debio 1347, they should be administered at least 2 hours after Debio 1347 administration.

9.2.3 Haematological support

- The use of red blood cell transfusions will be permitted as clinically indicated during the study.
- The use of bone marrow colony stimulating factors (such as granulocyte colony-stimulating factor or granulocyte-macrophage colony-stimulating factor) is permitted as clinically indicated. Prophylactic use is prohibited.

9.2.4 Infections

- CR-BSI (Catheter-Related Bloodstream Infection) should be managed according current Clinical Practice Guidelines⁴⁶.
- Febrile neutropenia: Antibacterial and antifungal prophylaxis for fever and treatment of neutropenia should be managed according the current Clinical Practice Guidelines^{47,48}.
- MSRA (Methicillin-Resistant Staphylococcus Aureus) infection should be managed according the current Clinical Practice Guidelines⁴⁹.

